10.4.2 Objective #2

Severity of diagnoses and laboratory values will be assigned according to predetermined definitions (see Appendix tables 4 and 5). A diagnosis (Appendix table 4) will be attributed to ampicillin if it was first made on a day that the infant was exposed to ampicillin. A laboratory abnormality (Appendix table 5) will be attributed to ampicillin if it occurred on a day that the infant was exposed to ampicillin or one day after exposure to ampicillin. For the cohort of patients from the PPRU Antimicrobial PK in High Risk Infants study enrolled at Reda, the frequency of diagnoses and laboratory abnormalities attributed to ampicillin will be described using standard summary statistics. For the patients exposed to ampicillin in the Pediatrix database, the frequency of diagnoses and laboratory abnormalities attributed to ampicillin will be compared to those not attributed to ampicillin. Multivariable logistic regression analyses will be performed to evaluate the association between diagnoses and laboratory abnormalities and ampicillin controlling for clinical factors associated with poor outcome in infants such as mechanical ventilation, inotropic support, and demographic features including race, gender, gestational and postnatal age. Outlier diagnostics and evaluation for multicollinearity will be performed using standard techniques. The full model containing all clinically relevant variables listed above will be compared to scaled down models using likelihood ratio tests, and the most parsimonious model that fits the data will be used for analysis. The odds of a diagnosis or laboratory abnormality occurring on a day the infant was exposed to ampicillin will be compared to the odds of occurrence on a day the infant was not exposed to ampicillin. Odds ratios and 95% confidence intervals derived from this model will be reported.

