6.1.2.2 Pediatrix Administrative Database Review

Data will be extracted from the Pediatrix Medical Group Database. The following clinical and demographic variables will be included in addition to date of birth, gestation age, race, ethnicity, sex, and birth weight (Table 3).

Table 3: Variables Collected for Pediatrix Safety Study

	Date of birth	-3 days	-2 days	-1 day	On ampicillin	+1 day	+2 days	+3 days
Adverse Events (new onset)								
Cardiorespiratory arrest					X			
Hypotension					X			
Tachypnea					X			
Tachycardia					X			
Medical NEC					X			
Surgical NEC					X			
Focal intestinal perforation					X			
Grade II IVH					X			
Grade III or IV IVH					X			
Periventricular leukomalacia					X			
Cystic periventricular leukomalacia					X			
PDA requiring medical treatment					X			
PDA requiring surgical treatment					X			
Rash					X			
Seizure					X			
ROP requiring laser surgery					X			
Hyperbilirubinemia requiring exchange transfusion					X			
Laboratory Values								
AST		X	X	X	X	X	X	X
ALT		X	X	X	X	X	X	X
GGT		X	X	X	X	X	X	X
Direct bilirubin		X	X	X	X	X	X	X
WBC count		X	X	X	X	X	X	X
Neutrophil count		X	X	X	X	X	X	X
Hematocrit		X	X	X	X	X	X	X
Platelets		X	X	X	X	X	X	X
BUN		X	X	X	X	X	X	X
Creatinine		X	X	X	X	X	X	X
Glucose		X	X	X	X	X	X	X
Sodium		X	X	X	X	X	X	X
Potassium		X	X	X	X	X	X	X
Calcium		X	X	X	X	X	X	X
Magnesium		X	X	X	X	X	X	X
Phosphorus		X	X	X	X	X	X	X
Base excess		X	X	X	X	X	X	X
Positive Blood/Urine/CSF Cultures								
Organism		X	X	X	X	X	X	X
Ampicillin Dosing								
Days of administration					X			
Clinical Variables								
Mechanical ventilation					X			
Fraction of inspired oxygen					X			
Concomitant medications					X			

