19 APPENDIX

Table 4. Diagnoses

Body System	Diagnoses	Serious Diagnoses
Gastrointestinal	Medical NEC	Surgical NEC
		Focal intestinal perforation
Neurologic	Grade II IVH	Grade III or IV IVH
	Periventricular leukomalacia	Cystic periventricular leukomalacia
		Seizure
Cardiovascular	PDA requiring medical treatment	PDA requiring surgical treatment
	Hypotension requiring pressors	Cardiorespiratory arrest
	Tachycardia	
Ophthalmology		ROP requiring laser surgery
Hematology		Hyperbilirubinemia requiring exchange transfusion
Dermatology	Rash	
Respiratory	Tachypnea	

IVH=intraventricular hemorrhage
 PDA=patent ductus arteriosus

NEC=necrotizing enterocolitis
 ROP=retinopathy of prematurity

Table 5. Laboratory Values

Laboratory Values	Abnormality	Serious Abnormality
Serum Electrolytes		
Hypoglycemia	< 40 mg/dL	< 20 mg/dL
Hyperglycemia	> 250 mg/dL	> 400 mg/dL
Hyponatremia	< 125 mmol/L	< 115 mmol/L
Hypernatremia	> 150 mmol/L	> 160 mmol/L
Hyperkalemia	> 6 mmol/L	> 7.5 mmol/L
Hypokalemia	< 3 mmol/L	< 2.5 mmol/L
Hypercalcemia (iCa)	> 12.5 mg/dL (>1.5 mmol/L)	> 13.5 mg/dL (>1.6 mmol/L)
Hypocalcemia (iCa)	< 6.0 mg/dL (<0.9 mmol/L)	< 5.0 mg/dL (< 0.8 mmol/L)
Hypermagnesemia	> 3.5 mg/dL	> 4.5 mg/dL
Hypomagnesemia	< 1.5 mg/dL	< 1.2 mg/dL
Hyperphosphatemia	> 9.5 mg/dL	> 10.5 mg/dL
Hypophosphatemia	< 3.5 mg/dL	< 2.5 mg/dL
Base Excess	< -10 mmol/L	< -15 mmol/L
Renal Dysfunction		
Elevated BUN	> 70 mg/dL	> 100 mg/dL
Elevated Creatinine	> 1.7 mg/dL	> 3.0 mg/dL
Liver Dysfunction		
Elevated AST	> 5 x upper limit of normal	> 10 x upper limit of normal
Elevated ALT	> 5 x upper limit of normal	> 10 x upper limit of normal
Elevated GGT	> 5 x upper limit of normal	> 10 x upper limit of normal
Direct bilirubin	> 5 mg/dL	>10 mg/dL
Complete Blood Count		
Leukocytosis	> 25,000/mm ³	> 40,000/mm ³
Leukopenia	< 5000/mm ³	< 2000/mm ³
Neutropenia	< 500/mm ³	< 100/mm ³
Thrombocytopenia	< 100/mm ³	< 30/mm ³
Thrombocytosis	> 600,000/mm ³	> 1,000,000/mm ³

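### The same-day attribution rule in 10.4.2 cannot be read as a drug effect for ROP requiring laser surgery, periventricular leukomalacia and cystic periventricular leukomalacia

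*Protocol*

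**What the plan says.** Section 10.4.2 of the protocol gives the rule for diagnoses: "A diagnosis (Appendix table 4) will be attributed to ampicillin if it was first made on a day that the infant was exposed" to the drug. There is no lag and no look-back. Laboratory abnormalities are treated a little more generously and count "if it occurred on a day that the infant was exposed to ampicillin or one day after exposure to ampicillin".

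Appendix Table 4 lists 17 diagnoses under this rule. They include "ROP requiring laser surgery" and "Cystic periventricular leukomalacia", both classed as serious, and periventricular leukomalacia (PVL), classed as non-serious.

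The attribution feeds three outputs in 10.4.2:

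- **PPRU chart review (about 60 infants):** attributed events are summarised.
- **Pediatrix, exposed infants:** "the frequency of diagnoses and laboratory abnormalities attributed to ampicillin will be compared to those not attributed to ampicillin". No adjustment is stated for this comparison.
- **Pediatrix, logistic model:** "The odds of a diagnosis or laboratory abnormality occurring on a day the infant was exposed to ampicillin will be compared to" the odds on an unexposed day. The covariates include "demographic features including race, gender, gestational and postnatal age", and the model may then be reduced by likelihood ratio tests.

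In Table 2 (section 6.1.2.1) and in the table headed "Table 3: Variables Collected for Pediatrix Safety Study" (section 6.1.2.2), adverse events are marked only in the on-ampicillin column.

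**The concern.** A same-day rule suits an event that appears during exposure and is recorded when it appears. For these three diagnoses, the recorded date may fall well after the process began. Laser-treated ROP is defined by an operation. For PVL, I assume that the date is that of the image that first shows it; the protocol gives no imaging schedule.

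An infant treated in the first week and diagnosed weeks later therefore enters the model as an event on an unexposed day. An infant who has laser surgery during an unrelated later course is counted against ampicillin. What the analysis measures is whether the procedure or image coincided with a treatment day.

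At stake is how a result near 1 would be read. Section 10.1.2 expects about 400,000 exposed and 300,000 unexposed infants, so such an estimate could come with a narrow interval and pass for evidence of safety on two serious outcomes.

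**Working it through.** The protocol gives no event rate, odds ratio or power for these outcomes, so there is no figure to reproduce. It also does not say at what ages ampicillin is given or these diagnoses are recorded. **All rates and windows below are assumptions.**

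**1. Can the rule see a delayed harm at a fixed postnatal age?**

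Let a share *e* of infants be exposed early, and let early exposure double the later daily risk from *h* to 2*h*. On a late day, ampicillin is being given with probability *n* = 0.02 to infants not exposed early, and with probability *x* = 0.02 or 0.03 to those exposed early.

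- Cases on ampicillin days: e·x·2h + (1−e)·n·h
- Ampicillin days: e·x + (1−e)·n
- Cases on other days: e·(1−x)·2h + (1−e)·(1−n)·h
- Other days: e·(1−x) + (1−e)·(1−n)

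Because *h* is small, the odds ratio (OR) is close to the ratio of the two case rates. For e = 0.5 and x = 0.03:

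- Cases on ampicillin days: 0.03h + 0.01h = 0.04h, over 0.025 days
- Cases on other days: 0.97h + 0.49h = 1.46h, over 0.975 days
- OR = (0.04/0.025) / (1.46/0.975) = 1.07
- Share of cases attributed = 0.04/1.50 = 2.7%

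| e | x | Same-day OR | Cases attributed |
|---|---|---|---|
| 0.5, 0.7 or 0.9 | 0.02 | 1.00 | 2.0% |
| 0.5 | 0.03 | 1.07 | 2.7% |
| 0.7 | 0.03 | 1.05 | 2.8% |
| 0.9 | 0.03 | 1.02 | 2.9% |

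The true risk ratio for early exposure is 2 in every row.

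**2. No drug effect, no adjustment.**

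Take days 1 to 100, with ampicillin on a share *e* of days 1 to 7 and a share *l* of later days. The overall share is p = (7e + 93l)/100. The crude OR is approximately the odds of ampicillin on days when the diagnosis can be recorded, divided by the odds of p.

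- *Recorded late (days 50–100 or 21–42), l = 0.02.* For e = 0.5, p = (3.5 + 1.86)/100 = 0.0536, so OR = (0.02/0.98) / (0.0536/0.9464) = 0.36. For e = 0.3 it is 0.49, and for e = 0.7 it is 0.28.
- *Recorded late, e = 0.5, l = 0.10.* p = 0.128, so OR = (0.10/0.90) / (0.128/0.872) = 0.76.
- *Use even over time.* OR = 1.00.
- *PVL first imaged on days 5–14.* Three of the ten days carry the early share. For e = 0.7 and l = 0.02, the share on those days is (2.1 + 0.14)/10 = 0.224 and p = 0.0676, so OR = (0.224/0.776) / (0.0676/0.9324) = 3.98. Over e = 0.3 to 0.7 the range is 2.8 to 4.0. With e = 0.5 and l = 0.10 it is 1.9.

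**3. No drug effect, adjusted for postnatal age.**

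Stratified by day, or by the bands up to 7, 8 to 28 and over 28 days, the Mantel-Haenszel OR is 1.00 in every scenario. For the three bands this relies on the assumed use being constant within each band. If diagnosis is twice as likely on ampicillin days at the same age (sicker infants, or antibiotics around a procedure), the adjusted OR is 2.00 with no drug effect.

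**The case against.** The strongest reply is that the reported odds ratios come from a model that controls for postnatal age, and that a prespecified on-treatment, new-onset definition is a legitimate choice whose limits are well understood. Both parts carry weight.

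A reader might infer that ampicillin will look protective for these outcomes, because treatment is early and diagnosis late. The documents do not support that for the reported odds ratios. Step 3 shows that the pure timing bias disappears once postnatal age is retained and adequately modelled. Age could in principle be dropped in the model reduction, but with about 700,000 infants (400,000 + 300,000) a strong predictor is unlikely to go. Its functional form may properly be left to the statistical analysis plan. Even the crude direction is not settled: step 2 gives values below 1 for late recording, above 1 for early PVL imaging, and 1.00 for even use.

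What survives is that adjustment does not repair the definition of exposure. Comparing infants of the same age by whether they are on ampicillin that day still ignores what they received earlier. Nor does the adjustment reach the frequency comparison or the PPRU summary.

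It may also be said that excluding these outcomes is itself a judgement about latency. It is, but a modest one: it requires only that the same day is the wrong window, not agreement on the right one.

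**Conclusion.** The point holds as one of interpretability. For three of 17 diagnoses, two of them serious, 10.4.2 fixes a rule under which neither the attribution nor the day-level odds ratio answers whether ampicillin affects the outcome. In the adjusted model the main fault is insensitivity: an OR of 1.00 to 1.07 when early exposure truly doubles late risk. Confounding on the day of diagnosis can still push the estimate away from 1. The unadjusted comparison of attributed with non-attributed frequencies can be biased either way.

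The sizes rest on assumed exposure shares and diagnosis windows. The structural point does not: the rule as written gives no credit to exposure that ended before the diagnosis was made. How much that matters for PVL depends on an assumed delay between injury and first recorded image. For ROP the dependence on a procedure is in the name of the outcome. The change is worth making because it is cheap. It does not affect the day-level analysis of the other 14 diagnoses.

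**What to change.** Add a sentence to 10.4.2 and a footnote to Appendix Table 4 stating that ROP requiring laser surgery, periventricular leukomalacia and cystic periventricular leukomalacia are excluded from:

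- same-day attribution, in both the PPRU chart review and Pediatrix;
- the comparison of attributed with non-attributed frequencies;
- the day-level odds ratios.

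Report their frequency per infant in the Pediatrix data descriptively, without attribution to ampicillin, and keep the day-level model for the other diagnoses. The per-infant count needs these diagnoses for the whole stay. The planned comparison with unexposed days needs that already, but Table 3 marks adverse events only on ampicillin and should be read or amended accordingly. Table 2 has the same restriction, so the PPRU review cannot supply such a count as it stands.

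The cost is one sentence, one footnote and no odds ratio for three of 17 diagnoses. An infant-level analysis by prior or cumulative exposure is a possible alternative. It would require choosing an exposure window and handling confounding between infants, and this fix does not depend on it.

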2 BACKGROUND INFORMATION AND SCIENTIFIC RATIONALE

2.1 Background Information

2.1.1 Ampicillin Therapy for Bacterial Sepsis in Infants

Bacterial sepsis remains a leading cause of death in infants admitted to neonatal intensive care units (NICUs). The incidence of early onset sepsis (<4 postnatal days) in infants admitted to the NICU is 1.2% to 2% and for late onset sepsis (4-120 postnatal days) 14% to 36%. The incidence of late onset sepsis is higher in very low birth weight infants (VLBW, birth weight <1500 g) [1,2]. The most commonly administered medication in the NICU, with an exposure rate of 693 per 1000 NICU-discharged infants, is ampicillin [3]. Ampicillin is a beta-lactam antibiotic approved by the FDA to treat local and disseminated infections caused by susceptible organisms in patients of all age groups [4].

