6.1.2 Objective #2

6.1.2.1 REDACTED PPRU Antimicrobial PK Study

Data will be extracted from the medical record of participants enrolled at Redacted in the PPRU Antimicrobial PK in High Risk Infants study. The following clinical and demographic variables will be included in addition to date of birth, gestation age, race, ethnicity, sex, and birth weight (Table 2).

Table 2: Variables Collected for Redacted Safety Study

	Date of birth	-3 days	-2 days	-1 day	On ampicillin	+1 day	+2 days	+3 days
Demographics								
Weight	X			X		X		
Length	X			X		X		
Head circumference	X			X		X		
Adverse Events (new onset)								
Cardiorespiratory arrest					X			
Hypotension					X			
Tachypnea					X			
Tachycardia					X			
Medical NEC					X			
Surgical NEC					X			
Focal intestinal perforation					X			
Grade II IVH					X			
Grade III or IV IVH					X			
Periventricular leukomalacia					X			
Cystic periventricular leukomalacia					X			
PDA requiring medical treatment					X			
PDA requiring surgical treatment					X			
Rash					X			
Seizure					X			
ROP requiring laser surgery					X			
Hyperbilirubinemia requiring exchange transfusion					X			
Laboratory Values*								
AST		X	X	X	X	X	X	X
ALT		X	X	X	X	X	X	X
WBC count		X	X	X	X	X	X	X
Hematocrit		X	X	X	X	X	X	X
Platelets		X	X	X	X	X	X	X
BUN		X	X	X	X	X	X	X
Creatinine		X	X	X	X	X	X	X
Physical Exam								
Abnormality				X	X			
Positive Blood/Urine/CSF Cultures								
Organism		X	X	X	X	X	X	X
Antimicrobial sensitivities		X	X	X	X	X	X	X
Ampicillin dosing**								
Date/time					X			
Dose (mg)					X			

* If laboratory value obtained on start day of ampicillin course, time of day should be recorded.

** Only start of/changes in/last dose of ampicillin dosing/frequency associated with the ampicillin course in which PK samples were obtained will be recorded.

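### Section 10.4.2 attributes to ampicillin laboratory abnormalities that pre-date the course and start-day diagnoses that may have prompted it

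*Protocol*

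**What the plan says.** Section 10.4.2 states both rules as definite definitions. The first covers the diagnoses in Appendix Table 4: each one "will be attributed to ampicillin if it was first made on a day that the infant was exposed to ampicillin". Under the second, an abnormal value from Appendix Table 5 is attributed "if it occurred on a day that the infant was exposed to ampicillin or one day after exposure to ampicillin".

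These rules feed two analyses. In the chart review of about 60 PPRU infants, attributed events are summarised as frequencies. In Pediatrix, attributed frequencies are compared with those not attributed, and the odds of an event on an exposed day "will be compared to the odds of occurrence on a day the infant was not exposed to ampicillin". The logistic regression is described as "controlling for clinical factors associated with poor outcome in infants such as mechanical ventilation, inotropic support", plus race, gender, gestational age and postnatal age.

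Tables 2 and 3 (sections 6.1.2.1 and 6.1.2.2) collect laboratory values on days -3, -2 and -1, on ampicillin, and on days +1 to +3. Adverse events are labelled as new onset and are marked only in the on-ampicillin column. A footnote to Table 2 adds: "If laboratory value obtained on start day of ampicillin course, time of day should be recorded". Table 3 has no such note and lists only days of administration for dosing.

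**The concern.** Section 2.1.1 presents ampicillin as treatment for bacterial sepsis, so infants are often ill when it is started. Two kinds of event can then be charged to the drug although it did not cause them.

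- **Laboratory values.** A low platelet or white-cell count present on day -1 and still present on the start day meets the rule. So does a start-day sample drawn before the first dose.
- **Diagnoses.** Necrotizing enterocolitis (NEC), intestinal perforation, hypotension requiring pressors, cardiorespiratory arrest or seizure may be the reason that treatment began. If first recorded on the start day, it counts as an ampicillin event.

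At stake are the frequencies reported as attributed to ampicillin and, for the second kind, an odds ratio that can point to harm where there is none.

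**Working it through.** **1. The rules against the data collected**

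| | Diagnoses | Laboratory values |
|---|---|---|
| Event counted | First made on an exposed day | Occurred on an exposed day or the day after |
| Earlier events excluded? | Yes | No |
| Start day separated? | No | No |
| Pre-course days in Tables 2 and 3 | None marked | Days -3 to -1 |
| Time of day on start day | None | Chart review only |

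The carry-over fault is confined to laboratory values. The start-day fault affects both. Section 10.4.2 uses neither the day -3 to -1 values nor the recorded start-day time to decide attribution.

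**2. Start-day diagnoses: size under assumed inputs**

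The protocol has no figure to reproduce, and every rate below is an assumption.

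*Model A.* The drug has no effect, the background daily risk is h, the start-day risk is k·h because illness triggers treatment, and the course lasts L days. Mean exposed-day risk m = h(k + L − 1)/L, and OR = [m/(1 − m)] / [h/(1 − h)]. Example with h = 0.001, k = 2, L = 3: m = 0.001 × 4/3 = 0.00133, so OR = 1.33.

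| OR, h = 0.001 | k = 2 | k = 5 | k = 10 |
|---|---|---|---|
| L = 2 | 1.50 | 3.01 | 5.52 |
| L = 3 | 1.33 | 2.34 | 4.01 |
| L = 7 | 1.14 | 1.57 | 2.29 |
| L = 10 | 1.10 | 1.40 | 1.90 |

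With h = 0.01 the values barely move (L = 3, k = 10 gives 4.12). With the start day set aside, the exposed-day risk is h and the OR is 1.00.

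*Model B.* Ampicillin is given on a share p of days for other reasons, and a share q of diagnoses triggers it the same day. The share of diagnoses on exposed days is s = p + (1 − p)q, and OR = [s/(1 − s)] / [p/(1 − p)].

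| OR | q = 10% | q = 25% | q = 50% |
|---|---|---|---|
| p = 15% | 1.74 | 3.22 | 7.67 |
| p = 25% | 1.44 | 2.33 | 5.00 |

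Both models give crude odds ratios. The protocol will report adjusted ones.

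**3. Laboratory carry-over: share of attributed events**

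Assume a fraction f is abnormal on day -1, with probability r of still being abnormal on the start day, and new onset at u = 0.01 per day over L + 1 days.

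Attributed proportion A = f[r + (1 − r)(1 − (1 − u)^L)] + (1 − f)[1 − (1 − u)^(L+1)]. Carried-over share = f·r/A.

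- f = 2%, r = 0.5, L = 3: A = 0.0103 + 0.0386 = 0.0489; share = 0.010/0.0489 = 20%.
- f = 10%, r = 0.8, L = 3: A = 0.0806 + 0.0355 = 0.1161; share = 0.080/0.1161 = 69%.
- The same two settings with L = 7: A = 0.0864 and 0.1509; shares 12% and 53%.

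Among infants with a normal value before the course, the attributed proportion is 1 − 0.99^4 = 3.9% (L = 3) or 1 − 0.99^8 = 7.7% (L = 7).

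**4. Direction of the laboratory odds ratio**

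Unless they belong to an earlier course, days -3 to -1 are unexposed days. A count that is low on day -2 and stays low therefore adds to the unexposed side as well as the exposed side. An abnormality that starts on treatment and outlasts day +1 also falls on unexposed days. The net direction cannot be settled from the protocol.

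**5. Adjustment**

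The named covariates do not include indication, start day or prior laboratory value. Adjustment also does not change which events are attributed.

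**The case against.** Several replies have force.

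- **Diagnoses made before treatment are already excluded.** This stands. A reader might infer that every pre-existing condition is charged to ampicillin, but the first-made wording and the new-onset label rule that out for diagnoses.
- **Pre-course data exist for only part of the problem.** This stands too. It is tempting to say that the data needed to remove the conditions behind treatment are already collected. That is true of laboratory values. Tables 2 and 3 mark no pre-course days for diagnoses, so the remedy there must rest on diagnosis and dosing dates.
- **Carry-over runs both ways in Pediatrix.** This stands, so an inflated laboratory odds ratio is not shown. The inflated frequencies are.
- **Only some diagnoses are affected.** Of the nine serious diagnoses in Table 4, a same-day trigger is plausible for about four: surgical NEC, focal intestinal perforation, arrest and seizure. Hypotension and medical NEC are in the non-serious column. No such mechanism is evident for, say, retinopathy needing laser surgery.
- **The magnitudes are invented.** They are assumptions, and adjustment for postnatal age may alter them. A claim that false signals will have very tight intervals is also unsupported: 400,000 exposed infants is a large number, but precision depends on event counts that the protocol does not give.
- **The study is descriptive, and a SAP may refine the rule.** Risk windows and sensitivity analyses often sit in a SAP. Here the protocol itself fixes a definite rule, and followed as written it misclassifies these events.

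**Conclusion.** The point holds in two parts.

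**Laboratory rule.** It counts abnormalities that pre-date the course and so inflates the attributed frequencies in both data sources. Under the assumed inputs, 12% to 69% of attributed abnormalities are carried over. The net effect on the Pediatrix odds ratio is uncertain.

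**Diagnosis rule.** It counts start-day illness that may have prompted treatment. Wherever that happens, the odds ratio for that diagnosis is biased toward harm, and the listed covariates do not remove the bias. With no drug effect, Model A gives 1.33 to 4.01 for a 3-day course and 1.14 to 2.29 for a 7-day course. Across all settings tried in both models the range is 1.10 to 7.67, and the top value needs half of all diagnoses to trigger treatment the same day.

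The faults follow from the text of section 10.4.2. The sizes rest on start-day risk, course length and abnormality prevalence, none of which the protocol states.

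**What to change.** 1. **Laboratory values.** Count an abnormality only if it is new, or of worse grade than any value in the preceding 3 days. Apply the same condition to exposed and unexposed days, because applying it to exposed days alone would bias the odds ratio toward protection. Tabulate infants with no prior value separately, for example those treated from birth. In the chart review, use the recorded time so that start-day values drawn before the first dose count as baseline. In Pediatrix, where no time is listed, report start-day values separately.
2. **Diagnoses in Pediatrix.** Classify start-day events apart from later exposed days, and report the odds ratio with and without the start day. First-day reactions, including rash and seizure, then stay visible.
3. **Diagnoses in the chart review.** Record the time of start-day diagnoses where it is available.

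The cost is revised wording in section 10.4.2, one time field for about 60 charts, and some extra analysis. The look-back on unexposed days needs laboratory values from the three days before each of them. Table 3 sets its grid around the course and stops at day -3, so the extraction may have to reach further. True first-day reactions will appear in a separate category.

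### Section 10.4.2 counts a laboratory abnormality on the day after ampicillin as an ampicillin event, but the logistic regression puts that day among the unexposed days

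*Protocol*

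**What the plan says.** Section 10.4.2 of the protocol sets the attribution rules and the regression contrast in one paragraph.

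- **Diagnoses, attribution.** A diagnosis "will be attributed to ampicillin if it was first made on a day that the infant was exposed to ampicillin". There is no extension to the following day.
- **Laboratory abnormalities, attribution.** The abnormality is attributed "if it occurred on a day that the infant was exposed to ampicillin or one day after exposure to ampicillin".
- **Frequency comparison, exposed Pediatrix infants.** Here "the frequency of diagnoses and laboratory abnormalities attributed to ampicillin will be compared to those not attributed to ampicillin". This comparison uses the attribution rules.
- **Regression.** One side of the contrast is "The odds of a diagnosis or laboratory abnormality occurring on a day the infant was exposed to ampicillin". On the reference side stand "the odds of occurrence on a day the infant was not exposed to ampicillin". One sentence serves both outcome types.
- **Reporting.** "Odds ratios and 95% confidence intervals derived from this model will be reported".

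Table 3 in section 6.1.2.2 records "Days of administration" for ampicillin. For laboratory values it has one column for time on ampicillin and separate columns for each of the three days after.

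**The concern.** The laboratory attribution rule and the regression classify the same calendar day differently. An abnormality on the first day after the last exposure counts towards ampicillin in the frequency comparison and towards the reference group in the odds ratio. The two Pediatrix laboratory results would then rest on different exposure windows, and nothing in the protocol tells the reader so.

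The odds ratios and their confidence intervals are the only inferential safety result that section 10.4.2 names. A laboratory window that includes the day after makes sense only if an effect can still show on that day. If it can, leaving the day in the reference group raises the reference risk and moves the odds ratio towards 1, the unwelcome direction in a safety study. Section 10.1.2 expects about 400,000 exposed infants, so intervals may be narrow and would not signal a shift of this kind.

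**Working it through.** **Step 1: the rules side by side.** The protocol states no event rate or odds ratio for this contrast, so there is no figure to reproduce. The first check is of definitions.

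| Day | Laboratory attribution rule | Regression sentence | Agree? |
|---|---|---|---|
| Ampicillin given | ampicillin | exposed | yes |
| First day after a course or gap | ampicillin | not exposed | **no** |
| Later drug-free days | not ampicillin | not exposed | yes |

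For diagnoses the first day after is outside the attribution window and also not exposed, so the rules agree. Inside a continuous course the next day is itself an exposed day, so no conflict arises there. The PPRU cohort gets summary statistics only, with no regression to disagree with.

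**Step 2: can exposed be read to include the day after?** The attribution sentence names the exposed day and the day after as two alternatives, so its own use of the word excludes the day after. Table 3 also separates the days. No other section defines an exposed day more widely.

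**Step 3: illustrative size.** Assumptions, none from the protocol:

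- baseline daily risk p0 = 0.02;
- risk p1 on exposed days, set by the true odds ratio;
- the effect persists at full strength on the day after;
- U further unexposed days per course at risk p0, with U = 3, 10 or 20;
- days pooled, with no covariates.

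With odds(p) = p/(1 − p):

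- aligned odds ratio = odds(p1) / odds(p0);
- odds ratio as written = odds(p1) / odds[(p1 + U × p0)/(U + 1)].

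Worked case, true odds ratio 2.0 and U = 3:

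- odds(p0) = 0.02/0.98 = 0.02041, so odds(p1) = 0.04082 and p1 = 0.03922;
- reference risk = (0.03922 + 3 × 0.02)/4 = 0.02480, with odds 0.02543;
- odds ratio as written = 0.04082/0.02543 = 1.60.

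| True odds ratio | U = 3 | U = 10 | U = 20 |
|---|---|---|---|
| 1.0 | 1.00 | 1.00 | 1.00 |
| 1.5 | 1.33 | 1.44 | 1.47 |
| 2.0 | 1.60 | 1.84 | 1.91 |

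**Step 4: which assumption matters.** For a rare outcome the formula reduces to OR × (U + 1)/(OR + U). For a true 2.0 this gives 2 × 4/5 = 1.60 at U = 3 and 2 × 21/22 = 1.91 at U = 20. The baseline risk has dropped out and course length never enters. The number of reference days drives the result.

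**The case against.** The strongest reply is that the regression sentence is a loose summary, written once for diagnoses and laboratory values, and was meant to follow the attribution rules above it. That is possible, but the text does not say so. Because the protocol states both rules, this is a conflict and not a detail left for an analysis plan.

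A second reply is that the effect is small. Section 4 speaks of all infants in the Pediatrix database, and section 10.1.2 anticipates 300,000 infants who did not receive ampicillin. If their days enter the reference group, one day per course is diluted. This stands, and it is why the size is shown as a range and as illustration only. Persistence at full strength through the day after is also assumed.

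Three stronger readings are tempting, and the protocol supports none of them.

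- *The mismatch inflates the estimate when there is no effect.* That would need events from the longer window divided by exposed days alone. Section 10.4.2 specifies no such rate. In the regression, an event stays in the same group as its day, so the null value remains 1.0.
- *Table 3 fixes the reference at six off-drug days.* Table 3 lists the days on which laboratory values are collected. It does not say that the regression is confined to them.
- *The frequency comparison is faulty because no denominator of days is named.* That is a reporting detail which an analysis plan, not shown here, may settle.

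**Conclusion.** The inconsistency is real and narrow. For Pediatrix laboratory abnormalities, the first unexposed day after a course or gap lies inside the attribution window and inside the regression's reference group. That conclusion rests on the wording alone.

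The consequence for the odds ratio is conditional. Without a drug effect there is no bias from this source. With an effect that lasts through the day after, the estimate is attenuated, modestly if reference days are many and by more if they are few. The figures in the working depend on assumed reference days and full persistence, so they show direction and order of size. They do not predict the study's result. It is worth settling before analysis, because otherwise the analyst must choose between two stated definitions with the data in hand.

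**What to change.** State one laboratory exposure window in section 10.4.2 and use it in both the attribution rule and the model. The choice that follows the protocol's own attribution rule is to code a laboratory day as exposed if ampicillin was given that day or the day is the first after the last exposure. The minimum is to exclude that first day after from the reference days and to say so. Keep exposed days only for diagnoses, where the rules already agree.

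The cost is one sentence and one derived variable, built from the days of administration already listed in Table 3. No new data are needed.
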